6.0 STUDY POPULATION

Prospective approval of protocol deviations to recruitment and enrolment criteria, also known as protocol waivers or exemptions, are not permitted.

6.1 Inclusion Criteria

Participants are eligible to be included in the study only if ALL of the following criteria apply:

Type of Participant and Disease Characteristics

- Male or Female
- Age ≥ 18 years
- Proven SARS-CoV-2 infection (confirmed by PCR from a nasopharyngeal or lower respiratory tract sample or antigen testing from a nasal sample)
- A score of Grade 3 to 5 on the WHO 9-point Ordinal Scale
- Male participants must agree to use a highly effective contraception as detailed in [Appendix 5](#) during the treatment period and for at least 4 days after the last dose of study treatment and refrain from donating sperm during this period
- Female participants are eligible to participate if not pregnant; not breastfeeding; and at least one of the following conditions is met:
 - Not a woman of childbearing potential as defined in [Appendix 5](#)

OR

- A woman of childbearing potential who agrees to follow the contraceptive guidance in [Appendix 5](#). During the treatment phase and for at least 4 days after the last dose of study medication
- Capable of giving signed informed consent which includes a commitment to comply with the requirements and restrictions listed in the informed consent form (ICF) and within this protocol.

6.2 Exclusion Criteria

Participants are excluded from the study if ANY of the following criteria apply:

Exclusion Criteria:

- 1) Patients who have previously had a score of 6 or 7 on the WHO 9-point Ordinal Scale
- 2) Patients who require support with invasive mechanical ventilation at the time of inclusion, or expected to be required within 24 hours of randomization

- 3) Alanine aminotransferase (ALT) OR aspartate aminotransferase (AST) $>2 \times$ the upper limit of normal (ULN) OR Total Bilirubin $>$ ULN. In patients with a documented history of Gilbert's Syndrome AND baseline total bilirubin elevation consistent with an exacerbation of Gilbert's Syndrome (i.e. no other cause of total bilirubin elevation), subjects may enroll if total bilirubin is <5 x ULN.
- 4) Diagnosis of liver cirrhosis, esophageal varices, ascites or hepatic encephalopathy
- 5) Chronic liver diseases such as autoimmune hepatitis, primary biliary cholangitis, primary sclerosing cholangitis, Wilson's disease, haemochromatosis
- 6) Significant renal disease or infection (as determined by the Investigator) including stage 4 chronic kidney disease or estimated glomerular filtration rate <60 mL/min
- 7) Absolute neutrophil count $\leq 1000/\mu\text{L}$ at screening
- 8) Myocardial infarction, transient ischemic attack or stroke within 3 months prior to the first dose
- 9) Current unstable angina or congestive heart failure (New York Heart Association III/IV)
- 10) Screening 12-lead EKG with a measurable QTc interval according to Fridericia correction (QTcF) >450 ms
- 11) Anticipated transfer to another hospital that is not the study center within 24 hours
- 12) Allergy to study medication or excipients
- 13) Inability to swallow tablets
- 14) Other documented comorbidities or laboratory abnormalities that in the opinion of the Investigator could affect the outcome of the study assessments, participant safety, or ability of the participant to comply with the requirements of the protocol
- 15) Any patient whose interests are not best served by study participation, as determined by the Investigator

Excluded Prior/Concomitant Therapy

- 16) Requirement for medications mainly metabolized by CYP2C9 and with narrow therapeutic index (eg, warfarin, phenytoin) is prohibited unless therapeutic monitoring available for duration of alvelestat dosing
- 17) Medicines that are potent CYP3A4 inhibitors including (but are not limited to) clarithromycin, diltiazem, erythromycin, itraconazole, ketoconazole, ritonavir, verapamil and potent inducers including but not limited to phenobarbital, phenytoin and rifampicin, will be exclusionary
- 18) Requirement for medications substantially reliant on OATP1B1 for metabolism where discontinuation during study drug administration is not possible or where fluctuations in levels are considered clinically important (as per investigator judgement) and cannot be clinically monitored (e.g., statins, valsartan, olmesartan, enalapril, repaglinide)

Excluded Prior/Concurrent Clinical Study Experience

19) Participation in any clinical investigation using investigational treatments within 4 weeks or 5 half-lives of the drug (whichever is longer) prior to the initial dosing (or longer if required by local regulations) is prohibited. Use of remdesivir (Veklury) or other COVID-19 therapies, including antibody treatment under the conditions of the authorization for emergency use in the US, and per manufacturer's instructions, is permitted.

6.3 Lifestyle Restrictions

6.3.1 Meals and Dietary Restrictions

There are no specific restrictions in respect of mealtimes and administration of study treatment.

6.3.2 Alcohol and Tobacco

Participants should avoid alcohol during the 5 or 10 days of study drug dosing.

6.3.3 Activity

Subjects should not participate in unaccustomed or more vigorous exercise than usual routine in the 48 hours before each blood sample for laboratory safety tests.

6.4 Screen Failures

Screen failures are defined as participants who consent to participate in the clinical study but are not subsequently randomized. A minimal set of screen failure information is required to ensure transparent reporting of screen failure participants to meet the Consolidated Standards of Reporting Trials (CONSORT) publishing requirements and to respond to queries from regulatory authorities. Minimal information includes demography, screen failure details, available eligibility criteria, and any SAEs. Individuals who do not meet the criteria for participation in this study (screen failures) may be rescreened after discussion with and approval of the Principal Investigator (PI).

Additionally, individual laboratory parameters or screening tests may be repeated, within the screening period, if the result is considered aberrant or not clinically consistent with the patient's health status. Decisions to re-test should be made in conjunction with the study PI.

7.0 TREATMENTS

Study treatment is defined as the investigational treatment alvelestat (MPH966).

7.1 Treatments Administered

There are no bioavailability data to support administration of alvelestat given dissolved in fluid or as broken/crushed tablets for administration via nasogastric or other enteric feeding tube. If participants are unable to swallow tablets orally, study drug treatment needs to be discontinued (Section 8.1).

Study Treatment Name:	30mg alvelestat tablets	Placebo
Dosage Formulation:	Tablet	Tablet (identical in appearance to active)
Unit Dose Strength(s) / Dosage Level(s):	Days 1-5 (or 10): 240mg bid (8 x 30mg tablets bid)	Days 1-5 (or 10): 8 x tablets bid
Route of Administration	Oral	Oral
Dosing Instructions:	To be taken bid, 12 hours apart	
Packaging and Labeling:	Study treatment will be provided in wallets and will be labeled as required per U.S. regulations.	
Manufacturer:	Mereo BioPharma 4 Ltd., [name]	

7.2 Method of Treatment Assignment

All participants will be randomized via a random allocation to alvelestat or placebo arms to meet enrolment needs of the study. The randomization numbers will be linked to the 2 treatment regimens, and the randomization scheme will not be stratified

7.3 Blinding

The placebo and alvelestat tablets are indistinguishable. This is double-blind study. The sponsor and principal investigator, will remain blinded to the study treatment allocation until the primary safety and efficacy assessment (based on Day 60 data). The site study team and participants will remain blinded until end of the study. The randomization list will be kept secure from the study team, Investigators, and participants throughout the conduct of the study and until unblinding is authorized by the PI.

7.4 Preparation/Handling/Storage/Accountability

Only participants enrolled in the study may receive study treatment, and only authorized site staff may supply or administer study treatment. All study treatments must be stored in a secure,

environmentally controlled, and monitored (manual or automated) area in accordance with the labelled storage conditions with access limited to the Investigator and authorized site staff.

The Investigator, institution, or the head of the medical institution (where applicable) is responsible for study treatment accountability, reconciliation, and record maintenance (i.e., receipt, reconciliation, and final disposition records).

Further guidance and information for the final disposition of unused study treatment are provided in the Manual of Procedures (MOP).

7.5 Treatment Compliance

The per-protocol dosage, timing, and mode of administration of study treatment may not be changed apart from dose titration to manage toleration. Any departures from the intended regimen must be recorded in the CRF

7.6 Concomitant Therapy

Treatment for COVID-19 disease, complications and co-morbidities

Treatment required for medical management of COVID-19 and co-morbidities is allowed throughout the study, apart from protocol defined prohibited medications. Other investigational treatments should not be started during the period of study follow up.

CYP2C9 Substrates

Alvelestat has a weak potential to inhibit CYP2C9. Therefore, medications that are metabolized mainly by CYP2C9 and have a narrow therapeutic index are prohibited unless regular blood monitoring can be provided. Narrow therapeutic index CYP2C9 substrates include warfarin and phenytoin (a complete list is included in the MOP or online at <http://medicine.iupui.edu/clinpharm/ddis/main-table>).

Enhanced clinical monitoring in patients receiving sensitive/moderate sensitive CYP2C9 for enhanced clinical effect should be considered. Moderate sensitive substrates include tolbutamide and glimepiride.

7.7 Treatment After the End of the Study

Alvelestat will not be provided after the end of the study.

8.0 DISCONTINUATION CRITERIA

8.1 Discontinuation of Study Treatment

In considering discontinuation of the study treatment, the Investigator should give particular consideration of the following:

Liver Test Abnormalities

The following monitoring schedule is proposed when a case of acute liver function abnormalities or worsening of a liver function abnormality is reported:

- 1) If ALT or AST increases to $>3 \times$ ULN but $<5 \times$ ULN, in participants with normal transaminases at baseline, repeat testing within 48 to 72 hours including ALT, AST, ALP and Total Bilirubin [TB], should be performed and query for symptoms made. If repeat testing shows ALT or AST persists $>3 \times$ ULN (alternatively 2-fold increase above baseline for participants with abnormal values before study drug exposure), close observation is to be initiated as follows:
 - Regular monitoring (twice to three times a week) is required (AST, ALT, ALP and TB)
 - Initiate potential DILI evaluation for alternative etiologies. Testing for alternative etiologies can include serology tests (hepatitis A, hepatitis B, hepatitis C, Cytomegalovirus (CMV), Epstein-Barr Virus (EBV), Herpes Simplex Virus (HSV), varicella zoster virus (VZV), parvovirus, toxoplasmosis), imaging, and pathology assessments (creatinine phosphokinase, clotting) as appropriate to the clinical situation. Consider a hepatology consult.
 - Follow the patient, if laboratory parameters stabilize or normalize the patient can continue on study treatment during this period.

If the increase in ALT or AST to $> 3 \times$ ULN is also in association with abnormalities in TB or INR or with clinical hepatitis as specified below, study drug **MUST** be stopped.

- 2) If AST or ALT are $\geq 5 \times$ ULN, a repeat value should be obtained within 24-48 hours. If the repeat ALT OR AST values is $\geq 5 \times$ ULN, the drug should be discontinued and the patient followed until the laboratory values normalize or stabilize, in addition to initiating potential (Drug Induced Liver Injury) DILI evaluation.
- 3) When the following abnormal liver test conditions are met, study treatment **MUST** be discontinued, the study PI be informed, and further steps discussed:
 - ALT or AST $>3 \times$ ULN and total bilirubin $>2 \times$ ULN **OR**
 - ALT or AST $>3 \times$ ULN and international normalized ratio (INR) >1.5 **OR**

- Any elevation in ALT or AST with clinical hepatitis: ALT or AST >ULN and the appearance of worsening fatigue, nausea, vomiting, right upper quadrant pain/tenderness, fever, rash, or eosinophilia
- Alkaline phosphatase >2x ULN and direct bilirubin >2 x ULN

4) When the following hepatic adverse events are met, study treatment **MUST** be discontinued, the study PI be informed, and further steps discussed:

- Regardless of the magnitude of the transaminase elevation, if the bilirubin is elevated (any level) in addition to the presence of signs and symptom(s) such as rash, eosinophilia, nausea, vomiting, or right upper quadrant pain
- INR ≥ 1.5 (unless due to therapeutic anti-coagulant use) and TB ≥ 2.5 x ULN, irrespective of the magnitude of ALT or AST elevation
- TB elevation ≥ 2.5 x ULN, and ALP ≥ 2.5 x ULN for cholestatic liver injury.

For each scenario, initiate potential DILI evaluation for alternative etiologies and consider a hepatology consult. Liver biopsy should be considered for DILI. The complete liver profile including PT/INR must be repeated within 48-72 hours after first abnormal value is obtained. Follow the patient until laboratory parameters stabilize or normalize. Study medication can be restarted only if an alternative etiology is “definitively” identified and liver tests have returned to baseline. Testing for alternative etiologies can include serology tests (hepatitis A, hepatitis B, hepatitis C, Cytomegalovirus (CMV), Epstein-Barr Virus (EBV), Herpes Simplex Virus (HSV), varicella zoster virus (VZV), parvovirus, toxoplasmosis), imaging, and pathology assessments (creatinine phosphokinase, clotting) as appropriate to the clinical situation.

Clinically significant liver function abnormalities should be reported as an AE/AESI.

EKG Abnormalities

If a clinically significant finding is identified (including but not limited to changes from baseline in QTcF after enrolment), the Investigator or qualified designee will determine if the participant can continue in the study and if any change in participant management is needed. This review of the EKG printed at the time of collection must be documented. Any new clinically relevant finding should be reported as an AE.

When the following EKG change conditions are met, study treatment **MUST** be discontinued, the study PI informed, and further steps discussed:

- Absolute QTcF >500 ms or >60 ms increase from baseline as confirmed with 3 consecutive EKGs taken in a 30-minute period with at least 5 minutes between each EKG. The mean of the 3 EKGs will be used for decision making.

Acute Kidney Injury (AKI)

Alvelestat is predominantly renally excreted and the effect of acute kidney failure on PK is unknown. Participants who develop AKI requiring dialysis or hemofiltration must have study drug discontinued.

Other Laboratory Parameters

Study treatment **MUST** be discontinued if the following laboratory parameters criteria are met:

- Absolute neutrophil count less than or equal to $0.5 \times 10^9/L$ on 2 consecutive repeat tests within 48 to 72 hours.

Other

Study treatment **MUST** be discontinued if the following other criteria are met:

- Significant safety issues (as judged by the Investigator). This includes AEs considered unacceptable by the patient and/or the Investigator
- Any other protocol deviation that results in a significant risk to subject's safety
- Pregnancy as confirmed by positive urine test at any time during the study
- Withdrawal of informed consent.
- Progression to intubation/mechanical ventilation or other circumstance where continued administration of study drug tablets by the oral route is not possible.

Participants may voluntarily discontinue investigational treatment for any reason at any time. Participant decision on discontinuation of study treatment does not imply an automatic withdrawal from the study.

Refer to the Schedule of Assessments (SoA) for data to be collected at the time of treatment discontinuation (EoT) and follow-up and for any further evaluations that need to be completed.

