In the Phase 2b COPD program, there were 14 reported events of raised ALT or AST to $\geq 3 \times$ ULN across the studied doses (alvelestat) 5, 20, and 60 mg bid); there were no cases of Hy's law during the treatment period. Although definitive evidence of dose relationship was lacking, there was a suggestion of an increased incidence of liver transaminase elevations in patients on alvelestat for which there were no definitive alternative explanations. The highest transaminase elevations occurred in the highest alvelestat dose (60 mg bid). Elevations in hepatic biochemistry

assessments (transaminases) observed in patients in the alvelestat studies were confounded by alcohol or by concomitant medication, but an effect of alvelestat cannot be excluded at this time. COVID-19 disease is frequently associated with mild elevations in transaminases with increases >ULN of 75% and 2XULN in 45% of hospitalized patients (Phipps et al 2020). Elevation in alkaline phosphatase and total bilirubin are uncommon, and severe liver damage/failure has not been reported to date (Tian & Ye 2020). However, patients may be on multiple medications with the possibility of drug-related hepatotoxicity and greater sensitivity to any potential effects of alvelestat. As mild elevations of transaminases are common, in order to assess for any hepatic effects in the target population, participants with transaminases up to 3X ULN will be eligible, but only if there is no elevation of bilirubin due to liver dysfunction. In summary, exclusion criteria for clinically relevant hepatic disease, close observation and frequent in-study monitoring, and study treatment discontinuation criteria are in place to protect the safety of the subjects and liver abnormalities are included as adverse events of special interest (AESI).

There were no other clinically relevant changes in clinical chemistry data in the completed studies with alvelestat. There were also no clinically relevant changes in urinalysis were observed in the completed studies with alvelestat. There were no changes in EKG or vital signs data that indicated a clear treatment effect of alvelestat. However, in light of the minor changes in QTc in the dog toxicology, exclusion criteria and regular EKG monitoring at the time of peak concentrations of study treatment and discontinuation criteria will be applied in the study. Clinically significant changes in EKG are also included as an AESI.

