9.5.3 Adverse Events of Special Interest

Some AEs, regardless of their severity or outcome, will be expedited due to the relevance for subject safety or study treatment safety profile. These events should be reported to safety reporting group within 24 hours, as indicated in [Appendix 4](#). The AESIs for alvelestat are:

- Liver function abnormalities defined as:
 - a) Any occurrence of (i) ALT or AST elevations $>5 \times$ ULN or (ii) ALT or AST $>3 \times$ ULN and total bilirubin $>2 \times$ ULN or INR >1.5 or the appearance of worsening fatigue, nausea, vomiting, RUQ pain/tenderness, fever, rash, or eosinophilia.
 - b) Any occurrence of $<5 \times$ ULN or ALT or AST $<3 \times$ ULN and total bilirubin $<2 \times$ ULN where the tests have been repeated within 48 to 72 hours and the elevation confirmed on at least 2 separate occasions.

For participant safety and to ensure that the hepatotoxic potential of the study treatment to be determined, a standardized procedure for identification, monitoring, and evaluation of liver events must be followed as outlined in [Section 9.4.4](#) and [Section 8.1](#).

- EKG

If a study subject experiences any of the following cardiovascular events, the event should be reported immediately as an AESI and the study treatment discontinued:

- a) Absolute QTcF >500 ms or >60 ms increase from baseline.
- b) Any clinically significant cardiac abnormality on EKG.
- Infection

Any new infection that requires the use of systemic antimicrobial treatment (antibiotics, anti-viral, anti-fungal, or anti-mycobacterial) should be investigated with clinically relevant diagnostic tests.

- Neutropenia

Absolute neutrophil count less than or equal to 500 per μ L on 2 consecutive repeat tests within 48 to 72 hours.

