6 DEFINITIONS

6.1 General

General clinical study definitions are listed in Table 2.

Table 2. COSTA clinical study general definitions.

Term	Definition for Study
Baseline	The most recent pre-dose assessment prior to first dose of study medication.
Clinical status assessment	Each assessment will be recorded as a number in the CRF based on the WHO Ordinal Scale status categories below. Where possible the timing of each assessment should be similar (i.e. morning or evening throughout). The Ordinal Scale is adapted from the WHO R&D Blueprint expert group which measures illness severity over time (https://www.who.int/blueprint/priority-diseases/key-action/COVID19_Treatment_Trial_Design_Master_Protocol_synopsis_Final_18022020.pdf) according to the following criteria: 
 0. Uninfected, no clinical or virological evidence of infection 1. Ambulatory, no limitation of activities 2. Ambulatory, limitation of activities 3. Hospitalized – mild disease, no oxygen therapy* 4. Hospitalized – mild disease, oxygen by mask or nasal prongs* 5. Hospitalized – severe disease, noninvasive ventilation or high flow oxygen* 6. Hospitalized – severe disease, intubation and mechanical ventilation 7. Hospitalized – severe disease, ventilation and additional organ support – vasopressors, renal replacement therapy, extracorporeal membrane oxygenation 8. Death
COVID disease severity	At baseline/randomization, the categorization of COVID-19 disease severity will be in accordance with the FDA's document: COVID-19: Developing Drugs and Biological Products for Treatment or Prevention Guidance for Industry (May 2020). 
 Mild disease (meeting all inclusion and no exclusion criteria): Symptoms of mild illness that could include fever, cough, sore throat, malaise, headache, muscle pain, gastrointestinal symptoms, without shortness of breath or dyspnea and no clinical signs indicative of moderate, severe, or critical severity.

Term	Definition for Study

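### The mandatory liver stops in 8.1 ignore the entry value, so patients admitted with raised ALT/AST or Gilbert's bilirubin can be forced off treatment with unchanged liver tests

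*Protocol*

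**What the plan says.** **Entry.** Protocol 6.2, exclusion 3, excludes ALT or AST above 2x ULN and total bilirubin above ULN. With a documented history of Gilbert's syndrome and a matching bilirubin elevation, "subjects may enroll if total bilirubin is <5 x ULN". Protocol 5.8 gives a different ceiling: it says transaminases up to 3x ULN are eligible.

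**Stopping.** Protocol 8.1, Liver Test Abnormalities:
- Item 1 covers rises above 3x ULN. For patients abnormal before dosing it offers an alternative test, a doubling of the baseline value. It closes by requiring a stop when a rise above 3x ULN "is also in association with abnormalities in TB or INR or with clinical hepatitis as specified below".
- Item 3 requires a stop at "ALT or AST >ULN and the appearance of worsening fatigue, nausea, vomiting, right upper quadrant pain/tenderness, fever, rash, or eosinophilia".
- Item 4 requires a stop, whatever the transaminase level, "if the bilirubin is elevated (any level) in addition to the presence of signs and symptom(s) such as rash, eosinophilia, nausea, vomiting".

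Items 3 and 4 contain no baseline provision, and item 4 does not mention Gilbert's syndrome.

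**Restart.** The text after item 4 allows treatment to resume if another cause is definitively established and liver tests are back at baseline. Section 8.1.3 rules out re-challenge when the 8.1 liver discontinuation criteria were met.

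**Reporting.** The liver AESI definition in 9.5.3, part (a), starts from ALT or AST above 3x ULN with bilirubin above 2x ULN, continuing "or INR >1.5 or the appearance of worsening fatigue, nausea, vomiting, RUQ pain/tenderness, fever, rash, or eosinophilia".

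**Endpoint.** The number and percentage discontinuing alvelestat to Day 5 or 10 is a primary endpoint in both documents. The SAP composite in 8.3 also counts early ending of treatment in the first 10 days.

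**The concern.** Section 5.8 explains that patients with mildly raised transaminases are admitted on purpose, because such values are common in COVID-19 and the trial wants to look for hepatic effects in this population. Items 3 and 4 of 8.1 then treat the same values as half of a mandatory stop. The other half is a symptom, and several of those listed are ordinary features of the disease: the SAP (6.1, Table 2) describes "Symptoms of mild illness that could include fever, cough, sore throat, malaise, headache, muscle pain, gastrointestinal symptoms".

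A patient can therefore enter at 1.5x ULN, stay at 1.5x ULN, have a worsening fever on Day 2, and have to stop. In the five-day schedule the safety blood draw after baseline falls on Day 5, so on Days 2 to 4 the entry value, or whatever routine care has measured, would decide.

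Such a stop says little about how alvelestat is tolerated. It still counts in the primary discontinuation endpoint, shortens exposure, and would look like a liver-related discontinuation. With 10 and 5 patients, one or two of these stops can dominate the result.

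**Working it through.** The plan states no figure for this point, so there is none to reproduce. The check has two parts.

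**1. Do the entry and stopping ranges overlap?**
- ALT/AST: exclusion 3 admits values above 1x and up to 2x ULN. Item 3 applies to everything above 1x ULN. The whole admitted abnormal range lies inside the stopping range.
- Bilirubin, Gilbert's syndrome only: exclusion 3 admits values above 1x and below 5x ULN. Item 4 applies to any elevation. Again the admitted range lies wholly inside.
- Symptoms: item 3 asks for the appearance of worsening symptoms, so a stable presenting symptom does not literally meet it. A new or worse fever, fatigue or nausea does. Item 4 asks only that a sign or symptom be present.

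**2. How many patients does the ALT/AST route touch?**

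Inputs:
- Protocol 5.8: "COVID-19 disease is frequently associated with mild elevations in transaminases with increases >ULN of 75% and 2XULN in 45% of hospitalized patients". The second figure is read as above 2x ULN. Both are assumed to describe this trial's population at entry, with the other eligibility criteria leaving them unchanged.
- Protocol 5.2: 10 patients on alvelestat and 5 on control.
- q, the chance that a listed symptom appears or worsens during dosing. The documents give no value. It is assumed to be 10% to 30% and unrelated to the entry ALT/AST.

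Share already above ULN among those passing the limit:
- above 1x but not above 2x ULN: 0.75 - 0.45 = 0.30
- passing the limit: 1 - 0.45 = 0.55
- share: 0.30 / 0.55 = 0.545

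Expected patients who meet the laboratory half at entry:
- alvelestat: 10 x 0.545 = 5.5
- control: 5 x 0.545 = 2.7
- all: 15 x 0.545 = 8.2

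Stops with unchanged liver tests among the 10 alvelestat patients. Expected number = 10 x 0.545q. Chance of at least one = 1 - (1 - 0.545q)^10.

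| q (assumed) | Expected stops | Chance of at least one |
|---|---|---|
| 10% | 0.5 | 43% |
| 20% | 1.1 | 68% |
| 30% | 1.6 | 83% |

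Weight of one stop: 1/10 = 10 percentage points on alvelestat and 1/5 = 20 on placebo. The SAP (5.4) instead gives 1:1 allocation with 7 to 8 per arm. One stop is then 1/8 to 1/7, or 12.5 to 14.3 points, in either arm.

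Sensitivity to the entry ceiling: if 3x ULN (5.8) applied in place of 2x, the share would be (0.75 - c)/(1 - c), where c is the unstated proportion above 3x ULN. For c from 0.45 down to 0 this runs from 54.5% to 75%, so the 2x ceiling gives the lower end.

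**The case against.** **The lead-in limits the rules.** Section 8.1 introduces its liver text as applying to acute or worsening abnormalities, and a value that has not moved is neither. This reading is possible. But the lead-in introduces a proposed monitoring schedule, whereas items 3 and 4 are separate, emphatic stop instructions, and item 3 speaks of any elevation. If the lead-in is meant to govern them, the text should say so.

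**The low threshold is deliberate caution.** Section 5.8 says a liver effect of alvelestat cannot be excluded and that these patients may be more sensitive. That may justify the rule. It does not tell the investigator how to apply it to a patient admitted above the threshold.

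**The outputs already show this.** Protocol 10.3 and SAP 8.3 and 8.5 provide for reasons for discontinuation, adverse events leading to discontinuation and subject listings. With 15 patients these would reveal much. They do not require the triggering criterion, or whether its laboratory part was met at baseline.

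**Stronger readings that the documents do not support:**
- *Section 8.1 gives two opposed thresholds for clinical hepatitis.* The closing sentence of item 1 defers to the later definition, and its above-3x ULN case is a subset of item 3. Nothing there says to continue below 3x ULN.
- *The AESI definition contradicts the stopping rule.* Section 9.5.3 is a reporting definition and need not share a stopping threshold. Its and/or string is ambiguous, and part (b) addresses lower, repeat-confirmed values. Whether the difference is intended is a fair question, no more.
- *Different sites would act differently.* The trial has one center.
- *A Gilbert's patient with nausea must stop at the first dose.* Item 4 speaks of hepatic adverse events. Appendix 4 does not count a non-worsening pre-existing condition, or expected symptoms of the disease studied, as an adverse event. The case is arguable.
- *The listed symptoms are simply those of COVID-19.* Overlap with the SAP list is partial: rash, eosinophilia and right upper quadrant pain are not in it.

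**Conclusion.** The conflict between entry and stopping criteria stands. As written, items 3 and 4 of 8.1 can require discontinuation of patients whom exclusion 3 knowingly admits, without any change in their liver tests. The ALT/AST route is the common one; the bilirubin route concerns only patients with Gilbert's syndrome.

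The 55% share rests on the figures in 5.8, read as stated above and assumed to hold in this population. The 43-83% rests in addition on an assumed symptom rate and should be taken as an illustration of scale.

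A reader might infer that the result is biased against alvelestat. It is not shown to be: the same rule applies in both blinded arms, so it raises both discontinuation rates and adds noise, with no known direction. The harm is to interpretability. In an unpowered pilot of 15 whose primary purpose is tolerability, a few stops of this kind could make up much of the discontinuation count and feed the SAP composite.

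**What to change.** **Protocol wording.** Reconcile:
- 5.8 and 6.2 on the transaminase ceiling for eligibility (3x against 2x ULN);
- exclusion 3, including the Gilbert's allowance, with 8.1 items 1, 3 and 4, so that the text states how each mandatory stop applies to a patient whose entry value already meets its laboratory component;
- the restart sentence in 8.1 with the bar on re-challenge in 8.1.3.

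Also state whether the different symptom-linked threshold in the 9.5.3 reporting definition is intended. The sponsor decides the clinical rule; none is proposed here.

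**Data and reporting.** Add a CRF field for the 8.1 criterion that triggered each stop. Report the primary discontinuation count twice by arm: with all stops, and without those whose laboratory component was already met at baseline.

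**Cost.** Wording changes, one CRF field and one table row. No extra procedures or patients.
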